9.3.2 Exclusion Criteria

Subjects who meet any of the following criteria will be excluded from this study:

1. Any neurological condition that may be contributing to cognitive impairment above and beyond that caused by the subject's AD pathology, including any co-morbidities detected by neurological examination or MRI
2. Modified Hachinski Ischemic Scale >4
3. History of transient ischemic attacks or stroke within 12 months of Screening
4. A history of epilepsy. Subjects with a history of seizures (not including a history of simple febrile seizures in childhood) within 10 years of Screening. Subjects with disturbance likely to be due to seizures within 5 years of Screening.
5. Significant pathological findings on the brain MRI at Screening, including but not limited to: more than 4 microhemorrhages (defined as 10 mm or less at the greatest diameter), any microhemorrhage which is symptomatic, a single macrohemorrhage greater than 10 mm at greatest diameter, an area of superficial siderosis, evidence of vasogenic edema, greater than 3 lacunar infarcts or a single infarct >2 cubic centimeters involving a major vascular territory, evidence of severe microangiopathy, evidence of cerebral contusion, encephalomalacia, aneurysms, vascular malformations, infective lesions or space-occupying lesions (however, lesions diagnosed as arachnoid cysts and <1cm in diameter at their greatest diameter need not be exclusionary) or brain tumors (eg, meningioma). (revised per Amendment 01)
6. Any psychiatric diagnosis or symptoms, (eg, hallucinations, major depression, or delusions) that could, in the opinion of the investigator, confound the MCI/Prodromal or mild to moderate AD diagnosis or could interfere with study assessments or procedures (revised per Amendments 01 and 02)
7. A score of ≥ 8 on the 15-item Geriatric Depression Scale (GDS) at Screening
8. Abnormally low serum vitamin B12 (<LLN) levels for the testing laboratory (if subject is taking vitamin B12 injections, level should be at or above the LLN for the testing laboratory) at Screening
9. Thyroid stimulating hormone above the normal range. Other tests of thyroid function with results outside the normal range should only be exclusionary if they are considered clinically significant by the investigator. This applies to all subjects regardless of whether or not they are taking thyroid supplements.
10. Subjects with hepatic impairment, with total bilirubin greater than 1.5 \times upper limit of normal (ULN) or International Normalized Ratio (INR) greater than 1.7 at Screening or Baseline. Subjects with Gilbert's syndrome need not be excluded.
11. Any contraindications to MRI or PET scanning, including cardiac pacemaker/ defibrillator or ferromagnetic metal implants (eg, in skull; cardiac devices

- other than those approved as safe for use in MRI scanners). Subjects who require sedation for MRI or PET scanning as per local guidelines need not be excluded.
12. Any contraindications to LP for CSF sampling (eg, lower spinal malformation on physical examination, local spinal infection or other abnormality, including but not limited to obesity). Only applicable to subjects consenting to CSF sample collection (revised per Amendment 02)
 13. Severe visual or hearing impairment that would prevent the subject from performing psychometric tests accurately
 14. History of Ig deficiency or other immunodeficiency disorders (including subjects known to be human immunodeficiency virus positive)
 15. Subjects with chronic viral hepatitis
 16. A history of tuberculosis (TB). Subjects with no history of TB will be tested for previous TB exposure (eg, positive tuberculin skin test, interferon gamma release assay or other locally accepted tests) and a positive test will be exclusionary.
 17. A history of ophthalmic shingles
 18. A history of ocular herpes simplex virus (HSV) infection
 19. Any live vaccine in the 3 months before randomization.
 20. Any active infection within the last 4 weeks prior to randomization. For such cases, the timing of randomization can be extended (up to 4 weeks) to allow the infection to resolve; psychometric tests (eg, MMSE, CDR) and safety laboratory tests conducted at Visit 2 must be repeated. (revised per Amendment 02)
 21. Any chronic inflammatory disease that is not adequately controlled or that requires systemic or ocular immunosuppressive or immunomodulatory therapy. Subjects with:
 - a. Seasonal or perennial allergic rhinitis, asthma or chronic obstructive pulmonary disease where the condition is considered to be stable and adequately controlled by inhaled steroids need not be excluded.
 - b. Hashimoto's thyroiditis but who are stable on thyroid replacement therapy and not on systemic immunosuppressive therapy need not be excluded.
 - c. Cutaneous manifestations of immunological disease that do not require systemic immunosuppressive therapy or systemic immunomodulatory therapy need not be excluded (topical steroid treatment is permitted).
 22. CD4 (T helper cells), CD8 (cytotoxic T cells), or CD19 (B cells) absolute counts below population-adjusted LLN at Screening or Baseline and confirmed by a repeat test conducted 1 week after the initial test. The population-adjusted LLN for CD4 (T helper cells), CD8 (cytotoxic T cells), and CD19 (B cells) absolute counts are 396, 157, and 74 cells/ μ L respectively. See [Appendix 5](#). (revised per Amendment 02)
 23. Ig (IgG, IgA, or IgM) levels below the LLN at Screening or Baseline, unless both the Investigator and the Medical Monitor agree that the finding is not clinically significant. The assessment of clinical significance will include, but not be limited to, evidence of clinical immunodeficiency. The discussion with the Medical Monitor should include a

- detailed review of medical history of infections, clinical and laboratory findings. (revised per Amendment 01)
24. Clinically significant deviation from normal in physical examination, vital signs, or clinically laboratory tests at Screening or Baseline
 25. A prolonged QT/ corrected QT interval (QTc) interval (QTc >450 msec) at Screening or Baseline as demonstrated by average QTc interval from triplicate ECGs. A history of risk factors for torsade de pointes (eg, heart failure, hypokalemia, family history of long QT Syndrome) or the use of concomitant medications that prolong the QT/QTc interval.
 26. Any other abnormality of the ECG at Screening or Baseline (including QRS >110 msec, abnormal electrical axis, PR interval >220 msec and conduction abnormalities) considered clinically significant by the investigator
 27. Left bundle branch block at Screening or Baseline
 28. Persistent heart rate <50 or >100 beats per minute (bpm) at Screening or Baseline
 29. Persistent systolic blood pressure (BP) >165 mmHg or <90 mmHg and diastolic BP >100 mmHg or <60 mmHg at Screening
 30. History of cardiac arrhythmias. Subjects with other heart diseases (eg, ischemic heart disease, clinically significant valvular heart disease) that are not stably and adequately controlled, or uncompensated heart failure (New York Heart Association Class III and Class IV)
 31. Type 1 or Type 2 diabetes mellitus that is not well controlled
 32. Malignant neoplasms within 5 years before Screening (except for basal or squamous cell carcinoma in situ of the skin, or localized prostate cancer that did not require systemic therapy; these do not exclude the subject). Subjects who had malignant neoplasms but who have had at least 5 years of documented evidence of no active disease before Screening need not be excluded.
 33. Medical conditions (eg, cardiac, respiratory, gastrointestinal, renal disease) that are not stably controlled, or which, in the opinion of the investigator(s), could affect the subject's safety or interfere with the study assessments
 34. Hypopigmentation conditions (eg, albinism and vitiligo). Diagnosis of an underlying disease causing hypopigmentation is not necessary for exclusion if the clinical presentation is consistent with such a condition. Hypopigmentation associated with scarring need not be exclusionary. (revised per Amendment 02)
 35. Known or suspected history of drug or alcohol dependency or abuse within 2 years before Screening, current use of recreational drugs or a positive urine drug test at Screening. Subjects who test positive in the urine drug screen need not be excluded if in the clinical opinion of the investigator, this is due to the subject taking prior/concomitant medications for a medical condition that is not exclusionary and not due to drug abuse.
 36. Has a "yes" answer to the C-SSRS suicidal ideation questions 4 or 5, or any suicidal behavior assessment within 6 months before Screening, at Screening, or at the Baseline Visit; or has been hospitalized or treated for suicidal behavior in the past 5 years before

Screening

37. Violations of the medical restrictions as specified in the Concomitant Medications section of the protocol
38. Planned surgery that requires general, spinal, or epidural anesthesia that would take place during the study. Planned surgery, which requires only local anesthesia and which can be undertaken as a day case without inpatient stay postoperatively, need not result in exclusion if in the opinion of the principal investigator this operation does not interfere with study procedures and subject safety.
39. Participation in any other interventional clinical study related to cognitive impairment within 6 months before Screening unless it can be documented that the subject was in a placebo treatment arm
40. Currently enrolled in another clinical study or used any investigational drug or device within 60 days or 5 half-lives of the investigational medication (whichever is longer) preceding informed consent
41. Hypersensitivity to the study drug or any of the excipients or to other BACE inhibitors, or to the PET tracer, or components of its formulation
42. Females who are lactating or pregnant (as documented by a positive beta-human chorionic gonadotropin [β -hCG] or human chorionic gonadotropin [hCG] test with a minimum sensitivity of 25 IU/L or equivalent units of β -hCG or hCG) at Screening or Baseline. A separate baseline assessment is required if a negative screening pregnancy test was obtained more than 72 hours before the first dose of study drug.
43. Females of childbearing potential who:
 - Had unprotected sexual intercourse within 30 days before study entry or who do not agree to use a highly effective method of contraception (eg, total abstinence, an intrauterine device, a double-barrier method [such as condom plus diaphragm with spermicide], a contraceptive implant, an oral contraceptive, or have a vasectomized partner with confirmed azoospermia) throughout the entire study treatment period or for 28 days after study drug discontinuation.
 - Are currently abstinent, and do not agree to use a double-barrier method (as described above) or refrain from sexually active during the study treatment period or for 28 days after study drug discontinuation.
 - Are using hormonal contraceptives but are not on a stable dose of the same hormonal contraceptive product for at least 4 weeks before dosing or who do not agree to use the same contraceptive during the study treatment period or for 28 days after study drug discontinuation.
 - (NOTE: All females will be considered to be of childbearing potential unless they are postmenopausal [amenorrheic for at least 12 consecutive months, in the appropriate age group, and without other known or suspected cause] or have been sterilized surgically [ie, bilateral tubal ligation, total hysterectomy, or bilateral oophorectomy, all with surgery at least 1 month before dosing]). (revised per Amendment 04)

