9.1.2.3 Follow-Up Period

All subjects, regardless of whether they complete all 18 months of treatment or discontinue study drug prematurely, will complete 4 posttreatment Follow-Up Visits: 2, 4, 8, and 12 weeks after the last dose of study drug. If clinically indicated, more frequent safety assessments can be conducted as part of unscheduled visits during the post-treatment Follow-Up Period. (revised per Amendment 04)

The end of the study will be defined as the date of the clinical database lock (ie, when all study data are collected and data validation is completed).

As required by some regulatory agencies, the following estimates are provided:

- The study will begin in Nov 2014 and is projected to end by Apr 2018. (revised per Amendment 05)
- The maximum estimated period for each subject on study is anticipated to be approximately 2 years.

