9.3 Selection of Study Population

Approximately 60 ($\pm 20\%$) eligible MCI/Prodromal or mild to moderate AD subjects will be randomized at approximately 35 sites in the United States (revised per Amendments 02 and 04). There will be no restriction to the number of subjects from either population.

Subjects who do not meet all of the inclusion criteria or who meet any of the exclusion criteria will not be eligible to receive study drug.

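### Exclusion 29 joins the systolic and diastolic limits with 'and', so read literally one persistently out-of-range pressure does not exclude a subject (minor; wrong as written)

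*Protocol*

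**What the plan says.** Section 9.3.2, no. 29, excludes subjects with: "Persistent systolic blood pressure (BP) >165 mmHg or <90 mmHg and diastolic BP >100 mmHg or <60 mmHg at Screening". The synopsis has the same sentence, so neither place clarifies the other. The opening line of Section 9.3.2 makes any single numbered criterion sufficient for exclusion. That rule works between items and does not say how the parts of no. 29 combine.

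Two other criteria could catch an abnormal blood pressure. No. 24 excludes for "Clinically significant deviation from normal in physical examination, vital signs, or clinically laboratory tests at Screening or Baseline". No. 33 covers medical conditions that are not stably controlled or that the investigator thinks could affect safety or the assessments. Neither gives a blood pressure limit.

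The eligibility text available is that of Version 7.0 (Amendment 05, 26 September 2016). Section 9.7.1 carries text revised under a later Amendment 06, but the Amendment 06 version of Section 9.3.2 is not shown. The point applies to the version at hand.

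**The concern.** No. 29 uses 'or' inside each pressure and 'and' between the two. Taken as ordinary English logic, a subject meets it only when systolic and diastolic pressure are both out of range. Isolated systolic or isolated diastolic abnormality, whether high or low, then falls outside the one criterion that sets numbers for blood pressure.

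A numeric limit is there to give every site the same rule. Section 9.3 says that "eligible MCI/Prodromal or mild to moderate AD subjects will be randomized at approximately 35 sites in the United States". If the sentence can be read in more than one way, the same screening pressure could be an automatic exclusion at one site and a judgement call at another. The primary objective is safety and tolerability, so the safety exclusions should be exact.

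**Working it through.** The plan states no figure to reproduce here. The check is one of logic, followed by a date calculation that bears on the remedy.

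**Step 1. Enumerate the readings.** Classify systolic pressure as low (<90), in range or high (>165), and diastolic as low (<60), in range or high (>100). This gives 3 × 3 = 9 combinations.

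- Both pressures must be out of range: 2 × 2 = 4 of 9 combinations are excluded.
- Either pressure suffices: 9 − 1 = 8 of 9 are excluded.
- Strict precedence ('and' binds before 'or'): systolic >165, or (systolic <90 with diastolic >100), or diastolic <60. This excludes 3 + 1 + 2 = 6 of 9.

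'Both' and 'either' disagree in exactly the 8 − 4 = 4 combinations where one pressure alone is out of range. Strict precedence excludes two of those four.

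| Persistent screening BP | Both needed | Either suffices | Strict precedence |
|---|---|---|---|
| 180/85 | not excluded | excluded | excluded |
| 120/110 | not excluded | excluded | not excluded |
| 85/65 | not excluded | excluded | not excluded |
| 120/55 | not excluded | excluded | excluded |

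The 'both' and strict-precedence readings each include a pair that cannot occur, systolic below 90 with diastolic above 100. This suggests that neither was meant.

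**Step 2. Look for the intended reading in the same list.** In no. 26 the words "PR interval >220 msec and conduction abnormalities" list alternatives, and so do the words "New York Heart Association Class III and Class IV" in no. 30. Both support 'either'. Against that, no. 22 uses 'and' as a true conjunction (a low count that is also confirmed on repeat), and no. 28, directly above no. 29, uses only 'or' for its two heart-rate limits. Usage in the list leans towards 'either' without settling it.

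**Step 3. Size of the pool.** The target is 60 ± 20%: 60 × 0.8 = 48 and 60 × 1.2 = 72 randomised subjects.

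**Step 4. Could new wording still affect enrolment?** Section 9.1.2.3 states: "The study will begin in Nov 2014 and is projected to end by Apr 2018". It also states: "The end of the study will be defined as the date of the clinical database lock". A completing subject needs 78 + 12 = 90 weeks, or 630 days, from first dose.

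- 30 April 2018 − 630 days = 8 August 2016.
- Table 7 allows ±10 days at Visit 18 and ±3 days at the Follow-Up Visits, so a subject could finish up to 10 + 3 = 13 days early. 8 August + 13 days = 21 August 2016.
- 21 August to 26 September 2016 (Version 7.0) is 36 days.

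Last visits must also precede database lock, which moves the date earlier still. On the projected end date, the last subject to complete was probably randomised before Version 7.0 was issued.

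**The case against.** The strongest reply is that a clinician would read no. 29 as two ranges, each of which excludes. Nos. 26 and 30 show the same loose use of 'and', and the 'both' reading includes an impossible pair. Nos. 24 and 33 would in any case make it hard to admit a subject with a persistent 180/85 or 120/110, and no. 24 applies at Baseline as well as Screening. Nothing in the document shows a site applying no. 29 differently. The text comes from a version later amended, and recruitment had probably closed.

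Most of this stands as an argument about weight. It does not remove the defect. Inferring the intended meaning from other items is what a numeric limit should spare sites from doing, and nos. 24 and 33 rest on judgement with no threshold.

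A reader might infer three stronger things that the document does not support:

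- **That the wording plainly lets 180/85 through.** It does on the ordinary reading, but strict precedence excludes that subject. The example that fails on both of these readings is 120/110.
- **That subjects with unsafe pressures were enrolled, or that sites diverged.** No screening pressures or counts are given, and the two judgement criteria could have excluded such subjects.
- **That the comparison between arms is biased.** The criterion acts before randomisation and no analysis uses it.

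**Conclusion.** The criterion is wrong as written, and the matter is minor. On its ordinary literal reading no. 29 does not exclude a subject with one persistently out-of-range pressure. The three readings exclude 4, 8 or 6 of the nine combinations. That either pressure should exclude is almost certainly the intent, which supports the correction.

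The consequence is limited to consistency of safety eligibility among 48 to 72 randomised subjects. How many breached only one limit cannot be derived from the document. No endpoint, analysis set, sample size or test is affected.

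The conclusion rests on the Amendment 05 eligibility text. The view that randomisation has probably closed rests on a projected end date, while Section 9.3 still speaks of randomisation in the future tense. The synopsis also gives a study period of about 32 months, which does not match the roughly 41 months from November 2014 to April 2018. The timing is therefore indicative only.

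**What to change.** In Section 9.3.2 and in the synopsis, replace no. 29 with:

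*Persistent systolic BP >165 mmHg or <90 mmHg, or persistent diastolic BP >100 mmHg or <60 mmHg, at Screening.*

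Repeating 'persistent' makes clear that it governs both pressures. In the unlikely event that both pressures were meant to be required, the text should say so explicitly.

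If randomisation has closed, list in the study report the randomised subjects whose screening pressures breached only one of the two limits. Table 6 already schedules vital signs at Screening, so this needs no new data collection.

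The cost is a few words in two places with routine amendment and ethics review, and possibly a few more screen failures. If enrolment is over, the cost is one short listing.

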9.3.3 Removal of Subjects from Therapy or Assessment

The investigator may discontinue study drug or withdraw the subject from the study at any time for safety or administrative reasons. The subject may decide to stop study drug or withdraw from the study at any time for any reason.

Subjects who discontinue taking study drug prematurely for any reason will undergo an ED Visit within 7 days of their last dose of study drug (see [Section 9.1.2.2](#)). Follow-Up Visits will also be scheduled 2, 4, 8, and 12 weeks after the last dose of study drug (see [Section 9.1.2.3](#)). (revised per Amendments 04 and 05)

The primary reason for discontinuation and all other reason(s) contributing to the subject's discontinuation from study drug(s) should be collected on the Subject Disposition eCRF page. In addition, the date of last dose of study drug(s) will be recorded on the Study Drug Dosing eCRF page. If a subject discontinues study drug and withdraws from the study at the same time, the ED Visit will be followed (see [Section 9.5.5](#)).

Safety-related criteria for discontinuation of study drug include the following:

- a. A study drug discontinuation threshold will be set based on absolute counts of CD4 (T helper cells), CD8 (cytotoxic T cells), or CD19 (B cells). The discontinuation threshold will be set at below the level of the population-adjusted LLN (CD4=396 cells/ μ L; CD8=157 cells/ μ L; and CD19=74 cells/ μ L), at a level that represents a greater risk of opportunistic infection in the treated population. (revised per Amendment 02) For CD4 (T helper cells) the discontinuation threshold is 250 cells/ μ L. For CD8 (cytotoxic T cells) and CD19 (B cells) the discontinuation thresholds are 150 cells/ μ L and 50 cells/ μ L, respectively. Any subject who has CD4 (T helper cells), CD8 (cytotoxic T cells), or CD19 (B cells) absolute counts below the discontinuation threshold as confirmed by a repeat test conducted within 1 week of the initial test but who has no clinical signs or symptoms of infection, will have study drug temporarily suspended for at least 2 weeks but no more than 4 weeks. During this period of study drug suspension, lymphocyte subset counts and complete blood count (CBC) with differentials will continue to be tested weekly until CD4 (T helper cells), CD8 (cytotoxic T cells), and CD19 (B cells) have all returned to greater than the population-adjusted LLN after which time study drug can be resumed. Testing of lymphocyte subset counts and CBC with differentials is required weekly for 4 weeks following resumption of study drug administration. Temporary suspension and rechallenge with study drug is only permitted once for any given subject. If the lymphocytes and CD counts do not return to greater than the population-adjusted LLN within 4 weeks from the start of temporary suspension the subject will need to be permanently discontinued from study drug. (revised per Amendment 04)
- b. Subjects with CD4 (T helper cells), CD8 (cytotoxic T cells), or CD19 (B cells) absolute counts between the population-adjusted LLN and the discontinuation threshold will have lymphocyte subset counts performed on a weekly basis. (revised per Amendments 02 and 04) During the early stages of the treatment period, where visits are conducted weekly (ie, Visits 4, 5, 6, and 7), lymphocyte subsets are already scheduled to be

measured on a weekly basis and so additional visits or blood draws are not required. (revised per Amendment 02) For these subjects, the decision as to whether the subject remains on study drug or is to be discontinued from study drug will be based upon clinical judgment and will take into account any clinical presentation in addition to the lymphocyte subset counts. These subjects may continue with treatment if there is no clinical evidence of infection. They will be discontinued from study drug if they have infections of a moderate to severe intensity (eg, subjects whose infections are not localized, or are systemically unwell, or who require systemic anti-infective drug treatment).

Table 1 Study Drug Actions for Lymphocyte Subset Absolute Counts

| Lymphocyte subset absolute counts | Action | Decision to continue, discontinue, or temporarily suspend study drug |
|---|--|--|
| CD4 (T helper cells), CD8 (cytotoxic T cells), or CD19 (B cells) absolute counts below discontinuation threshold and no clinical signs or symptoms of infection | Retest within 1 week along with CBC with differentials | If retest performed within 1 week confirms lymphocyte subset counts below the discontinuation threshold, temporarily suspend study drug for between 2 and 4 weeks. Continue weekly testing of lymphocyte subsets and CBC with differentials. Rechallenge with study drug allowed when CD4 (T helper cells), CD8 (cytotoxic T cells), and CD19 (B cells) absolute counts all greater than population-adjusted LLN. Temporary suspension and rechallenge permitted only once for each subject. |
| CD4 (T helper cells), CD8 (cytotoxic T cells), or CD19 (B cells) absolute counts between population-adjusted LLN and discontinuation threshold | Lymphocyte subset counts (and CBC with differentials) to be performed weekly until lymphocyte subset counts return to \geq population-adjusted LLN | Decision will be based upon lymphocyte subset counts and clinical judgment |

LLN = lower limit of normal, CBC = complete blood count.

(Table revised per Amendments 02 and 04)

- c. Subjects with clinical evidence of infection will have their CD4 (T helper cells), CD8 (cytotoxic T cells), and CD19 (B cells) absolute counts measured. Blood and other biological samples will also be collected for investigations of infective pathogens (eg, serological tests, quantitative polymerase chain reaction, microscopy, and culture) where appropriate. In subjects with infection, if any of their absolute cell counts meets the discontinuation thresholds, study drug will be discontinued. All subjects with severe infections will be discontinued from study drug. All subjects with herpes zoster

(shingles) or ocular herpes infections will be discontinued from study drug, regardless of severity of presentation. Subjects with mild or moderate infection may continue treatment with study drug unless otherwise clinically indicated or otherwise specified below. Specifically, when any of the CD4 (T helper cells), CD8 (cytotoxic T cells), and CD19 (B cells) absolute counts are between the population-adjusted LLN and the discontinuation thresholds, subjects with infections of moderate intensity will be discontinued from study drug (eg, subjects whose infections are not localized, or subjects who are systemically unwell, or who require systemic anti-infective drug treatment). All subjects with infection who are discontinued from study drug will be followed for a period of 12 weeks or until the infection resolves/ stabilizes or until the CD4 (T helper cells), CD8 (cytotoxic T cells), and CD19 (B cells) absolute counts have returned to greater than population-adjusted LLN (whichever comes latest). (revised per Amendments 02 and 04)

Table 2 Study Drug Actions for Lymphocyte Subset Absolute Counts and Infection

| Criterion | Severity of Infection | | | |
|--|--|---|---|------------------------|
| | None | Mild | Moderate | Severe |
| CD4 (T helper cells), CD8 (cytotoxic T cells), or CD19 (B cells) absolute counts below discontinuation threshold | If confirmed with repeat testing within 1 week, then temporarily suspend study drug as per instructions above. | Discontinue study drug | Discontinue study drug | Discontinue study drug |
| CD4 (T helper cells), CD8 (cytotoxic T cells), or CD19 (B cells) absolute counts between population-adjusted LLN and discontinuation threshold | May continue treatment with study drug unless discontinuation is clinically indicated | May continue treatment with study drug unless discontinuation is clinically indicated | Discontinue study drug | Discontinue study drug |
| CD4 (T helper cells), CD8 (cytotoxic T cells), or CD19 (B cells) absolute counts always > population-adjusted LLN | May continue treatment with study drug unless discontinuation is clinically indicated | May continue treatment with study drug unless discontinuation is clinically indicated | May continue treatment with study drug unless discontinuation is clinically indicated (See (e) for exception) | Discontinue study drug |

LLN = lower limit of normal.

(Table revised per Amendments 02 and 04)

- d. A subject with any skin rash of moderate to severe intensity, or any rash lasting more than 72 hours regardless of severity (see (e) for exception), will be discontinued from study drug and a dermatological consult will be requested regardless of whether the rash is considered drug-related or due to other causes. For cases where the investigator suspects a drug rash, regardless of severity, the subject will be discontinued from study

drug, a dermatological consult will be requested, and a skin biopsy will be performed to confirm the diagnosis. The skin rash will be treated as per standard care and will be followed up until resolution regardless of etiology or severity.

- e. Subjects who develop moderate to severe oral or genital herpes should be discontinued from study drug. Subjects who develop a mild case of oral or genital herpes may remain on study drug even if the event lasts more than 72 hours.
- f. Development of any of the following features on MRI: vasogenic edema, macrohemorrhage, an area of superficial siderosis, or a symptomatic microhemorrhage. If discontinued from study drug, subjects will undergo an ED Visit within 7 days after discontinuation and will attend the Follow-Up Visits 2, 4, 8, and 12 weeks after the last dose of study drug. They will also undertake an Unscheduled Visit (with MRI) at approximately 4 weeks after the visit at which such MRI features were first identified. An MRI will also be performed at approximately the time of the final Follow-Up Visit (Visit 20). Additional visits for safety may be arranged if clinically indicated in the opinion of the investigator, including after 12 weeks after the last dose of study drug. At any time during the treatment period, subjects who have asymptomatic, treatment-emergent microhemorrhages as detected by MRI, but none of the features which merit discontinuation of treatment (ie, vasogenic edema, macrohemorrhage, an area of superficial siderosis, or a symptomatic treatment-emergent microhemorrhage) may continue with treatment. These subjects will have safety assessments (including MRI) at approximately 4 weeks after the visit at which such MRI features were found. They will also continue with the scheduled MRI scans. Additional unscheduled MRI scans may be arranged on an individual subject basis in discussion with the study medical monitor. (revised per Amendment 04)
- g. A postdose ECG with an average QTcF interval >500 msec from triplicate ECGs
- h. A postdose ECG with a QTcF interval increase from baseline >60 msec and a QTcF interval >450 msec as demonstrated from triplicate ECGs
- i. Any seizure (motor or non-motor)
- j. Pregnancy

